9.2.4 Clinical decision making

Once the results of the pathological evaluation of the prostate biopsies are available, - in consultation with the patient - the treating physician (or treatment team) will decide the further clinical management. If the decision for treatment is made and the patient decides to receive prostatectomy at our institution (Michigan Medicine), an effort will be made to analyze the location of tumor lesions within the resected prostate specimen and to register pre-biopsy PET and MRI imaging with pathology. If feasible, the prostate specimen may undergo additional (research) MRI to facilitate the registration process ⁵⁵.

9.2.5 Image interpretation and correlation with standard of truth

PET and MR imaging will be assessed visually. Abnormalities found on MRI and ⁶⁸Ga-PSMA PET will be selected as targets for image-guided biopsies.

Once prostate biopsies are obtained, the location of each biopsy is retrospectively associated with a matching region on pre-biopsy imaging (facilitated via image co-registration) and semi-quantitative PET data are obtained and compared with the standard of truth (Gleason score histology). Accordingly, we will determine whether a selected target was true positive, false positive, true negative or false negative on imaging (MRI and ⁶⁸Ga-PSMA PET) relative to pathological proof. Please note that the location (in 3D space) of a given biopsy core is known from ALL biopsies, whether obtained as standard or targeted core. This is possible because the navigated ultrasound workstation (i.e. UroNav, Invivo) used will record the biopsy core location (trajectory and core length within the gland) in 3D for all cores obtained ^{55,56}.

Accordingly, the sensitivity and specificity for the detection of low-grade (Gleason 3+3) and significant PCa (Gleason \geq 3+4) is determined for both modalities, ⁶⁸Ga-PSMA PET (based on uptake measures) and mpMRI (based on PI-RADS scores).

9.3 Lesion localization variables

9.3.1 Overall lesion localization rate

The total number of focal lesions detected on ⁶⁸Ga-PSMA PET/CT images will be recorded and compared to mpMRI.

9.3.2 Cancer lesion localization rate

The number of cancer lesions, as verified in histopathology, detected will be recorded and compared with co-localized lesions on ^{68}Ga -PSMA PET and mpMRI.

9.3.3 Visual assessment of lesion contrast and scoring

The investigator will visually assess the ^{68}Ga -PSMA PET/CT images. Using a scoring system (no increased uptake = 0, mild uptake = 1, moderate uptake = 2, high uptake = 3, relative to background) the accumulation of ^{68}Ga -PSMA in each target volume will be assessed.

9.3.4 Extra-prostatic lesions

We will also determine frequency and location of ^{68}Ga -PSMA positive lesions. Such lesions could be extra-prostatic tumor extension, lympho-nodal and/or distant metastatic disease not identified by conventional (standard) imaging. As clinically indicated (clinical relevance, accessibility, risk), an attempt will be made to obtain pathological proof of such lesions. The decision for or against a biopsy is made by the treating physician in consultation with the patient, and not demanded by the study.

9.3.5 Semiquantitative assessment: SUV, SUVR

The standardized uptake value (SUV) is defined as follows:

$$\text{SUV} = \text{activity (Bq/cm)} / [(\text{body weight (g)}) / \text{injected activity (Bq)}]$$

An even distribution of the tracer in the body results in an SUV = 1.

SUVRs can be obtained by calculating the ratio of SUV in a lesion and the SUV of a corresponding reference tissue, such as non-cancerous/non-inflammatory tissue of the same organ, blood, or muscle.

9.4 Adverse event monitoring

The presence of any pre-administration event (baseline signs and symptoms present just before radiotracer administrations) will be recorded in the CRF.

The following information will also be recorded in the CRF:

- The date of evaluation
- The onset time
- The resolution time or duration
- Action taken
- Status of symptom
- Intensity

Of these events, only events that increase in intensity after radiotracer administrations will be recorded as AEs in the CRF.

9.4.1 Adverse events

For this study, an AE is defined as any untoward medical occurrence in a clinical investigation subject after administration of the radiopharmaceutical products. An AE does not necessarily have to have a causal relationship with administration of the radiopharmaceutical product. An AE can therefore be any unfavorable and unintended sign (including an abnormal laboratory finding), symptom, or disease temporally associated

with the use of ^{68}Ga -PSMA, whether considered related to that product, or not. Only symptoms/signs that begin or worsen in severity and/or frequency after ^{68}Ga -PSMA administration/use will be recorded as AEs in the CRF.

The AE profile of ^{68}Ga -PSMA in humans has been established. No major adverse events have been reported in the literature. Therefore, major adverse events are extremely unlikely to occur. However, study personnel will remain vigilant at all times to the occurrence of AEs, particularly those that may be life-threatening. Personnel who are trained in the acute management of anaphylaxis and other emergencies and who have access to appropriate clinical supplies will be immediately available while the subject is confined to the study center. Treatment of serious AEs (SAEs) will consist primarily of the support of vital functions.

The subjects will be closely observed and questioned for any kind of AE during the study procedures and at follow-up appointments throughout the study period with non-leading questioning (e.g., "How do you feel?"). The subjects will be instructed to immediately report any symptoms and signs to the study staff (i.e., between formal observations).

9.4.2 Serious adverse events

An SAE is defined as any AE that:

- Results in death
- Is life-threatening
- Requires in-patient hospitalization or prolongation of existing hospitalization
- Results in persistent or significant disability or incapacity
- Is a congenital anomaly or birth defect
- Is another important medical event.*

(*Other important medical events are those that may not result in death, be life-threatening, or require hospitalization, but may be considered an SAE when, based upon appropriate medical judgment, they may jeopardize the subject and may require medical intervention to prevent one of the outcomes listed above.)

9.4.3 Adverse event and serious adverse event reporting

All AEs should be recorded using acceptable diagnoses, if possible. If an AE has already been reported, it is not necessary to report each individual sign and symptom of that AE as a separate AE. Grade refers to the severity of the AE. The CTCAE displays Grades 1 through 5 with unique clinical descriptions of severity for each AE based on this general guideline:

Grade 1 Mild; asymptomatic or mild symptoms; clinical or diagnostic observations only; intervention not indicated.

Grade 2 Moderate; minimal, local or noninvasive intervention indicated; limiting age-appropriate instrumental ADL.

Grade 3 Severe or medically significant but not immediately life-threatening; hospitalization or prolongation of hospitalization indicated; disabling; limiting self care ADL.

Grade 4 Life-threatening consequences; urgent intervention indicated.

Grade 5 Death related to AE.

SAEs will be recorded in the CRF if they occurred as follows:

- After a subject first received ^{68}Ga -PSMA and throughout the subject's follow-up period*, whether or not the AEs considered related to the tracer injections, and
- After the subject's follow-up period, if a causal relationship to ^{68}Ga -PSMA cannot be ruled out.

(*Follow-up period is defined as the protocol-stipulated period or, for subjects prematurely withdrawn from a study, the duration of a subject's participation.)

All serious and non-serious AEs must be followed for a final outcome until the end of the follow-up period. An outcome of "unknown" is not considered to be an acceptable final outcome. An outcome of "not yet resolved" is an acceptable final outcome for non-serious AEs at the end of a subject's participation in a study, and for SAEs at database lock.

The PI will report all SAEs to local health authorities, the IRB, and investigators as required by local regulations.

9.4.4 Expedited reporting

Expedited Reporting to the Food and Drug Administration

As the study is being conducted under an IND, the Sponsor-Investigator is responsible for determining whether or not the suspected adverse reaction meets the criteria for expedited reporting in accordance with Federal Regulations (21 CFR §312.32).

The Investigator must report in an IND safety report any suspected adverse reaction that is both serious and unexpected. The Sponsor-Investigator needs to ensure that the event meets all three definitions:

- Suspected adverse reaction
- Unexpected
- Serious

If the adverse event does not meet all three of the definitions, it should not be submitted as an expedited IND safety report.

The timeline for submitting an IND safety report to FDA is no later than **15 calendar days** after the Investigator determines that the suspected adverse reaction qualifies for reporting (21 CFR 312.32(c)(1)).

Any unexpected fatal or life-threatening suspected adverse reaction will be reported to FDA no later than **7 calendar days** after the Investigator's initial receipt of the information (21 CFR 312.32(c)(2)).

Any relevant additional information that pertains to a previously submitted IND safety report will be submitted to FDA as a Follow-up IND Safety Report without delay, as soon as the information is available (21 CFR 312.32(d)(2)).

9.5 Other variables

9.5.1 Demographic data

The subject's demographic data (gender, age, ethnicity and race, weight, height) will be recorded at screening.

9.5.2 Medical and surgical history

The subject's relevant medical and surgical history (i.e., a condition that is either active at enrolment or adversely impacts the subject's medical condition at enrolment) will be recorded at screening. Also, relevant

medical and surgical history may be viewed and recorded from digital patient records and optionally obtained from physicians involved in the care of the subjects.

9.5.3 Prior and concurrent medication

Information about medications taken by the subject during the study period will be recorded.

9.5.4 Appropriateness of measurements

All assessments and measurements are considered appropriate and regarded as standard medical practice.

10 DATA HANDLING AND QUALITY ASSURANCE

10.1 Clinical data management

All adverse events will be followed with appropriate medical management until resolved. Patients removed from study for unacceptable adverse events will be followed until resolution or stabilization of the adverse event. For selected adverse events for which administration of the investigational drug was stopped, a re-challenge of the subject with the investigational drug may be conducted if considered both safe and ethical by the Investigator.

This trial will be monitored in accordance with the NCI approved University of Michigan Rogel Cancer Center Data and Safety Monitoring Plan. The study team will meet every 3 months or more frequently depending on the activity of the protocol. The discussion will include matters related to the safety of study participants (SAE/UaP reporting), validity and integrity of the data, enrollment rate relative to expectations, characteristics of participants, retention of participants, adherence to the protocol (potential or real protocol deviations) and data completeness. At these regular meetings, the protocol specific Data and Safety Monitoring Report form will be completed and signed by the Principal Investigator or by one of the designated co-investigators.

Data and Safety Monitoring Reports will be submitted to the University of Michigan Rogel Cancer Center Data and Safety Monitoring Committee every 3 months for independent review.

10.2 Archiving

All study documentation at the investigators' site will be archived for a minimum of 7 years following completion or discontinuation of the study.

11 STATISTICAL METHODS AND PLANNED ANALYSIS

11.1 General statistical considerations

Statistical analysis will be performed as specified in the statistical analysis plan.

All subjects who complete the study without major changes versus protocol will be included in the evaluation of pharmacodynamics / pharmacokinetics.

11.2 Subject characteristics

A table will be provided with the following information:

- Number of subjects enrolled
- Number of subjects included in the efficacy analysis
- Number of subjects withdrawn from the study and the reason for withdrawal.

Demographic information (age, height, weight) will be summarized using descriptive statistics.

Medical histories will be summarized by counts and percent. Concurrent medications will be recorded and coded using a standard classification system and grouped by primary and secondary classes, if applicable.

11.2.1 Demographic and other baseline characteristics

Summary statistics (arithmetic mean, standard deviation, median, minimum and maximum for quantitative variables) will be presented. Frequency tables for qualitative data will be provided. Medical history findings will be summarized.

11.2.2 Pharmacodynamical data

Quantitative data will be described by the following summary statistics: arithmetic mean, standard deviation, median, minimum and maximum. Frequency tables will be provided for qualitative data.

11.2.3 Development of decision rules

Since mpMRI has already been performed prior to ^{68}Ga -PSMA PET/CT, and since suspicious lesions have been found and rated according to PI-RADS, the addition of ^{68}Ga -PSMA can lead to a) a change or confirmation of the mpMRI-defined PI-RADS risk score of a given lesion, or b) identification of additional lesions not identified on mpMRI. Since mpMRI has a high sensitivity, but relative low specificity for significant PCa, we anticipate that modification of the mpMRI risk score will be the main source for a change in management.

Currently, all PI-RADS 3, 4 or 5 lesions found at mpMRI are targeted for biopsy. Particularly problematic is that while PI-RADS 3 lesions are very frequent, their probability for significant PCa disease is low. The second most likely outcome, PI-RADS 4, has a roughly 50% chance to result in significant disease. If absence of ^{68}Ga -PSMA uptake in such lesions is associated with lack of significant disease, hybrid ^{68}Ga -PSMA PET/MRI could replace invasive biopsy procedures and avoid side effects for prostate biopsies in many men. On the other hand, if focally elevated ^{68}Ga -PSMA uptake would be found to correlate with significant disease, such potentially lethal disease could be found at earlier time points and with higher precision. Accordingly, the data are acquired to subsequently develop an evidence-based decision rule to inform which patients would a) benefit from a prostate biopsy procedure, and b) benefit most from ^{68}Ga -PSMA in addition to mpMRI.

12 STATISTICAL EVALUATION

Accrual potential: At the University of Michigan, over 800 patients receive a prostate biopsy per year (812 in 2016, 652 in 2015, 444 in 2014). The number of navigated TRUS-MRI fusion (targeted) prostate biopsies is rapidly increasing and reached 310 in 2016. In 2016, the Department of Radiology performed 960 mpMRI studies, of which about 60% (576) had a PI-RADS score ≥ 3 .

Prevalence of significant PCa: Among all patients with PI-RADS score ≥ 3 , the incidence of Gleason $\geq 3+4$ PCa is 15% for PI-RADS 3, 55% PI-RADS 4, and 80% PI-RADS 5. At our center, the sensitivity/specificity for Gleason $\geq 3+4$ is 96.5/59.7% for PI-RADS ≥ 3 , and 78.9/78.9% for PI-RADS ≥ 4 . The patient population for this trial will closely resemble a recently retrospectively investigated surveillance population from 2 centers in the state of Michigan (n=207) of men with clinical stage T1/T2 Gleason 3+3 PCa. The distribution of PI-RADS grading was as follows (unpublished data): PI-RADS 1-2 (37%), PI-RADS 3 (19%), PI-RADS 4 (31%), PI-RADS 5 (13%). This incidence of PI-RADS scores ≥ 3 is used in **Table 1** to estimate the incidence of Gleason 3+3 vs. $\geq 3+4$ vs. benign findings in the trial population. Since we will only select patients with prior mpMRI resulting in PI-RADS 3-5, we will be able to select a specific relevant patient population with a sufficient risk for significant disease (defined as Gleason $\geq 3+4$ PCa).

Disease incidence in study population: We estimate the potential impact of molecular imaging in addition to mpMRI for this trial on the basis of our prior ^{18}F -choline PET/MRI trial.¹⁶ Our final (submitted) data included 90 PI-RADS 3-5 lesions in 56 subjects resulting in 30 “positive” (Gleason $\geq 3+4$) and 60 “negative” (Gleason 3+3 or benign). Using a logistic regression model with two predictors—MRI suspicion score and a ^{18}F -choline lesion-to-background ratio of ≥ 1.58 (AUC = 0.95)—strongly favored the combined model over the mpMRI model alone (AUC = 0.83, $p < 0.001$). The selection of all PI-RADS ≥ 4 lesions for the prediction of Gleason $\geq 3+4$ PCa resulted in an excessive number of false-positive ($n = 27$ [FP]) and false-negative ($n=3$ [FN]) cases. When selecting PI-RADS 5 lesions only, 3 FP and 11 FN cases would have resulted, which indicates missing too many significant cancers. The addition of ^{18}F -choline PET to mpMRI resulted in 5 FP and 5 FN cases.

Compared to the selection of all PI-RADS ≥ 4 lesions (high sensitivity, poor specificity), the combined ^{18}F -choline PET/MRI model resulted in an improvement of the specificity by +38% with only a modest reduction in sensitivity (-10%). Implementation of this rule would have reduced the number of targeted lesions for biopsy by roughly 50% (from 51 to 25), exemplifying the cost-saving potential of a PET/MRI strategy. Given that ^{68}Ga -PSMA and ^{18}F -choline have different molecular targets (^{68}Ga -PSMA has higher specificity for PCa than ^{18}F -choline), and that the ^{18}F -choline trial investigated a high-risk patient population, these ^{18}F -choline results are not directly transferable to the use of ^{68}Ga -PSMA PET/MRI such as is being investigated in this proposal. Furthermore, any future ^{68}Ga -PSMA PET/MRI rule would likely be constructed differently. For sample size estimates in this trial, we therefore project conservatively that the sensitivity of mpMRI would minimally increase (by 2%, mainly from correctly identifying significant cancers rated as PI-RADS 3), while the specificity would increase by only 15%. Given the known superiority of ^{68}Ga -PSMA over ^{18}F -choline, as well as the known increase of PSMA-expression with increasing aggressiveness (Gleason scoring), we have no reason to assume that the performance of ^{68}Ga -PSMA would be inferior to ^{18}F -choline for the identification of significant PCa. As a result, these sample size estimates are quite conservative.

In conclusion, we are confident that the necessary number of subjects can be recruited with sufficient prevalence of significant PCa in this trial. The inclusion criteria will ensure a sufficient potential for positive imaging findings with ^{68}Ga -PSMA PET/CT, and a very high probability of successful targeting with image-guided biopsy.¹⁶

Table 1. Estimated incidence of Gleason 3+3 vs. $\geq 3+4$ vs. benign biopsy results in the trial population

Maximum PI-RADS risk score per subject	Number of subjects (%)	No prostate cancer Benign %	Total maximum grade Gleason = 3+3 %	Total maximum grade Gleason $\geq 3+4$ %
3	30	16 (53%)	10 (33%)	5 (17%)
4	49	9 (27%)	13 (27%)	26 (53%)
5	21	1 (5%)	3 (14%)	17 (81%)
Total (N)	100	26	26	48

Primary objective: Mixed-effects logistic regression is used to evaluate the primary objective, the diagnostic performance of mpMRI and PET. The outcome is Gleason $\geq 3+4$ or not, and predictors are PI-RADS v.2 score and ^{68}Ga -PSMA PET uptake. We employ a mixed effects model to account for within-subject correlation among one or more biopsied lesions. We will test the null hypothesis that the regression coefficient of PET is equal to zero versus an alternative hypothesis that it is not equal to zero, assessing whether ^{68}Ga -PSMA PET is an important factor to identify aggressive PCa. We also compare predictive accuracies of (1) PI-RADS ≥ 3 only and (2) PI-RADS ≥ 3 plus ^{68}Ga -PSMA PET models by examining the confidence intervals of a predictive performance measure: positive likelihood ratio (positive LR).

Secondary objectives: We are not expecting any adverse events related to the administration of the radiotracer. However, frequency tables will be generated to display the safety profile of ^{68}Ga -PSMA (secondary objective).

We will also record the frequency and location of extra-prostatic ^{68}Ga -PSMA positive lesions (such as extra-prostatic extension, lympho-nodal and/or distant metastatic disease) not identified by conventional (standard) imaging. Formal statistical evaluation is not planned as the frequency of such findings is expected to be low.

Exploratory objective: We will evaluate whether radiomics classifiers (obtained from mpMRI and ^{68}Ga -PSMA identified targets) could improve identification and risk stratification of significant PCa. Reference standard will be pathology defined as targeted plus standard prostate biopsy, and prostatectomy, when available. The performance of the different classifiers in detecting significant PCa will be evaluated by using the area under the receiver-operating characteristic (ROC) curve (AUC) using pathology as gold standard.⁵⁷

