7.2 Inclusion criteria

Male subjects (≥ 18 years of age) with prior mpMRI (within 3 months of recruitment) resulting in at least one PI-RADS 3-5 lesion with clinical need for a prostate biopsy procedure can participate, if one of the 2 criteria apply:

- Known Gleason 6 (3+3) or 7 (3+4, 4+3) prostate cancer undergoing active surveillance or in the confirmation phase of active surveillance,
- or
- Rising PSA with either a) no prior biopsy or b) single or multiple negative prior biopsies.

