12.1 Sample size determination

Sample size calculation was made for the primary objective only. We assess potential differences between the predictive performances of the two models (1) and (2), while maintaining ethical and economic considerations. We consider the positive likelihood ratio (positive LR) as a performance measure, which is defined by a ratio of sensitivity to 1-specificity. A higher positive LR means greater predictive information of positive test results irrespective of disease prevalence. Based on preliminary data obtained from mpMRI, we assume that the sensitivity and specificity of model (1) are both given by 0.789. For model (2), we assume conservatively that the sensitivity will be increased by 0.02 (2%) and that the specificity would improve by 0.15 (15%). In this scenario, the positive LR of model (1) is given by 3.74 and the positive LR of model (2) is calculated as 5.02. In order to detect the 1.28 difference in positive LR between the two models, we need at least 100 subjects, including at least 38 of 100 subjects with a histological diagnosis of significant PCa. The sample size was estimated as described in the literature.⁵⁸

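### The mpMRI comparator is written as PI-RADS ≥3, which every enrolled subject meets, but planned with PI-RADS ≥4 figures that no reading yields in a PI-RADS 3-5 population

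*Combined protocol and SAP*

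**What the plan says.** Section 5 and the synopsis set the primary outcome: whether the positive likelihood ratio (LR+, sensitivity divided by 1 − specificity) of PSMA PET/MRI is at least 1.28 above that of standard-of-care mpMRI.

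**Analysis.** Under Primary objective, section 12 models Gleason ≥3+4 on PI-RADS score and PET uptake, with mixed effects to "account for within-subject correlation among one or more biopsied lesions". It then says: "We also compare predictive accuracies of (1) PI-RADS ≥ 3 only and (2) PI-RADS ≥ 3 plus" PSMA PET, judged by confidence intervals for LR+.

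**Planning.** In section 12.1, "we assume that the sensitivity and specificity of model (1) are both given by 0.789", giving LR+ 3.74. Section 12 reports the centre's accuracy for Gleason ≥3+4 as "96.5/59.7% for PI-RADS ≥ 3 , and 78.9/78.9% for PI-RADS ≥ 4". It expects the small sensitivity gain from PET to come "mainly from correctly identifying significant cancers rated as PI-RADS 3".

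**Enrolment.** Under section 7.2, men with a prior mpMRI "resulting in at least one PI-RADS 3-5 lesion with clinical need for a prostate biopsy procedure can participate". Section 12 repeats the restriction: "Since we will only select patients with prior mpMRI resulting in PI-RADS 3-5".

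**Unit.** Section 12.1 counts subjects. Section 12.5.2 reports accuracy both per subject and per lesion, and lists neither LR+ nor the combined reading. Section 9.2.5 classifies selected targets, but also notes that the position of every core, targeted or standard, is recorded.

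**The concern.** Two things do not fit together. The cut-off in the analysis text (≥3) is not the cut-off behind the planning figures (≥4). In addition, enrolment removes the men who would be negative at ≥3, so specificity measured where such men or sites were included cannot be carried over to this trial.

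This matters because the primary criterion is an absolute difference in LR+. What a difference of 1.28 means depends on the baseline from which it is measured, and that baseline depends on a cut-off and a unit of analysis that the plan does not settle. The study is also open-label (section 8.3), so leaving the choice until the data are in hand would be hard to defend.

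**Working it through.** **1. The plan's own figure.** LR+ = sensitivity / (1 − specificity). Section 12.1: 0.789 / 0.211 = 3.74, as stated. This pair is the centre's ≥4 pair. The centre's ≥3 pair gives 0.965 / 0.403 = 2.39. The gain expected from cancers rated PI-RADS 3 points the same way, since they can add sensitivity only if PI-RADS 3 counts as negative on mpMRI alone.

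**2. The ≥3 rule as written, under each reading.**
- *Per subject.* From Table 1 (48 of 100 with Gleason ≥3+4, 52 without), everyone is positive: sensitivity 48/48 = 1, specificity 0/52 = 0, LR+ = 1.00.
- *Per lesion or core.* PI-RADS 3-5 lesions are all positive. LR+ can differ from 1 only through mpMRI-negative units. PET-only targets (sections 9.2.1 and 12.5.2) and standard-core sites (section 9.2.5) could supply these, but no rule says which enter the comparison.
- *Regression on the PI-RADS score, with ≥3 describing the lesion set.* No threshold turns the fitted model into a positive or negative test, so LR+ cannot be computed.

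**3. The ≥4 rule within PI-RADS 3-5.** If no mpMRI-negative units count:

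| Source | Sensitivity | 1 − specificity | LR+ | Share of 3.74 |
|---|---|---|---|---|
| Table 1, per subject | (26+17)/48 = 0.896 | (9+13+1+3)/52 = 0.500 | 1.79 | 48% |
| Centre figures conditioned on ≥3 | 0.789/0.965 = 0.818 | 0.211/0.403 = 0.524 | 1.56 | 42% |
| Prior choline trial, per lesion, 27 false positives | 27/30 = 0.90 | 27/60 = 0.45 | 2.00 | 53% |
| Same trial, 51 lesions selected, so 51 − 27 = 24 false positives | 27/30 = 0.90 | 24/60 = 0.40 | 2.25 | 60% |

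Some Table 1 rows do not add up to the row size, but the column totals do (26, 26, 48). As a check, row sizes 30/49/21 with section 12's incidences of 15/55/80% give (26.95+16.8)/48.25 = 0.907 and (22.05+4.2)/51.75 = 0.507, again LR+ 1.79. The two choline counts both come from section 12 and are shown as a range.

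**4. What 1.28 then means.** It is 1.28/3.74 = 34% of the planned baseline, but 1.28/2.25 = 57% to 1.28/1.56 = 82% of the baselines in step 3, and 128% of a baseline of 1.00.

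**5. Why the combined rule must be fixed too.** From Table 1, PI-RADS 5 alone gives (17/48)/(4/52) = 4.60. Against 1.79 that is a difference of 2.81, more than 1.28, with no PET information used.

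**The case against.** The best defence is that LR+ 1.00 joins the cut-off in one place to the unit in another. The LR+ comparison follows directly on a model for biopsied lesions, and the per-subject results in section 12.5.2 do not list LR+. The phrase may also just name the lesions analysed: PI-RADS score is a predictor, and the choline precedent was a logistic model fitted in PI-RADS 3-5 lesions. This stands to the extent that a reader who infers that the comparator simply has specificity 0 goes beyond the documents. That result belongs to the per-subject reading alone. The other readings still leave LR+ undefined, and none returns 3.74.

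The plan also says that the choline results do not transfer directly. That is fair, and they are used here only as the plan's sole per-lesion data in a PI-RADS 3-5 set. The per-subject figures do not depend on them.

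It can further be said that ≥3 is the proper standard-of-care comparator, since section 11.2.3 describes all PI-RADS 3-5 lesions as currently targeted. Which cut represents standard of care is indeed the sponsor's choice, but planning must then use the same cut.

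Finally, a reader might infer that 3.74 is what results once the 37% of PI-RADS 1-2 men in the surveillance cohort are added back to Table 1. The documents do not support this. The centre figures' source population is not stated. The sum reaches 3.74 only if about 1% of those men are assumed to have significant cancer. The components then disagree: sensitivity 0.885 at ≥4 against 0.789, and specificity about 0.53 at ≥3 against 0.597. What can be said is narrower: a specificity of 59.7% at ≥3 requires that mpMRI-negative units were counted.

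**Conclusion.** The plan is wrong as written on this point. The comparator is defined at ≥3 and planned at ≥4, and the planned LR+ of 3.74 is not obtained under any reading of the text in a PI-RADS 3-5 population. At ≥4 the plan's own figures give about 1.6 to 2.3, roughly 40-60% of 3.74. At ≥3 the value is 1.00 per subject and undefined otherwise. The 1.28 difference therefore does not carry its planned meaning.

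The range assumes that no mpMRI-negative units enter the comparison and that Table 1 is a fair projection. The 1.56 also assumes that both centre pairs come from one population; the 2.00 to 2.25 borrows from a different tracer and a higher-risk group.

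The test of the PET regression coefficient is not affected, so the conclusion concerns the named primary outcome and its sample-size statement, not every primary analysis.

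**What to change.** In section 12 (Primary objective), 12.1 and 12.5.2:
- Use the same mpMRI positivity cut-off and the same unit of analysis for planning and analysis. PI-RADS ≥4 versus 3 is the cut that the planning figures imply. If ≥3 is kept to represent standard of care, a per-subject LR+ carries no information; the analysis must then be per lesion or per core, with a definition of which mpMRI-negative units count.
- Fix the combined PET/MRI positivity rule in advance, so that a gain in LR+ cannot come from a stricter PI-RADS cut alone.
- Replace 0.789/0.789 with values for the chosen cut-off and unit in a PI-RADS 3-5 population (for ≥4 per subject, about 0.90/0.50 from Table 1). Then recompute the target LR+ difference and restate what the existing 100 subjects can show.

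This concerns the analysis only, not which lesions are biopsied. The cost is protocol and SAP wording and a redone planning paragraph, with no new procedures. The drawback is a less favourable stated baseline LR+.
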